7. CONDUCT OF STUDY ASSESSMENTS AND PROCEDURES

7.1. Administration of Informed Consent Form

A valid informed consent must be obtained from the study subject before any study-specific procedures are conducted using an ICF approved by the local IRB/IEC that contains all elements required by ICH E6 and describes the nature, scope, and possible consequences of the study in a form understandable to the study subject. Local and institutional guidelines for ICF content and administration must be followed; the original signed ICF must be retained by the investigator, and a copy of the signed ICF must be provided to the study subject. The informed consent process for each subject must be documented in writing within the subject source documentation.

7.2. Interactive Response Technology Procedure

The IRT will be contacted to obtain a subject ID number when a subject enters screening. Upon determining that the subject is eligible for study entry, the IRT will be contacted to obtain the treatment assignment. Additionally, the IRT will be contacted at each regular study visit to update the study drug supply. See appropriate information in Section [5.1.1](#).

7.3. Demography and Medical History

7.3.1. Demographics and General Medical History

Demographic data and general medical history will be collected at screening.

7.3.2. Disease Characteristics and Treatment History

A disease-targeted medical and medication history will be collected at screening.

7.4. Prior and Concomitant Medications and Procedures

Prior and concomitant medications and procedures will be reviewed to determine subject eligibility. All concomitant medications and measures must be recorded in the eCRF, and any medication received or procedure performed within 28 days before first dose and up to the end of study will be recorded in the eCRF. The medication record will be maintained after signing the ICF to document concomitant medications, including any changes to the dose or regimen. Concomitant medications include any prescription, over-the-counter, or natural/herbal preparations taken or administered during the study period. Concomitant treatments and/or procedures that are required to manage a subject's medical condition during the study will also be recorded in the eCRF.

7.5. Safety Assessments

7.5.1. Adverse Events

Adverse events will be monitored from the time the subject signs the ICF. Subjects will be instructed to report all AEs during the study and will be assessed for the occurrence of AEs throughout the study. In order to avoid bias in eliciting AEs, subjects will be asked general,

nonleading questions such as "How are you feeling?" All AEs (serious and nonserious) must be recorded on the source documents and eCRFs regardless of the assumption of a causal relationship with the study drug. The definition, reporting, and recording requirements for AEs are described in Section 8.

7.5.2. Physical Examinations

Clinically notable abnormalities that are considered clinically significant in the judgment of the investigator are to be reported as AEs.

Physical examinations must be performed by a medically qualified individual such as a licensed physician, physician's assistant, or an advanced registered nurse practitioner, as local law permits.

Clinically notable abnormalities that are considered clinically significant in the judgement of the investigator are to be reported as AEs.

7.5.2.1. Comprehensive Physical Examination

The comprehensive physical examination will include height (at screening) and body weight and assessment(s) of the following organ or body systems: skin; head, eyes, ears, nose, and throat; thyroid; lungs; cardiovascular system; abdomen (liver, spleen); extremities; and lymph nodes, as well as a brief neurological examination.

7.5.2.2. Targeted Physical Examination

The targeted physical examination will be a symptom-directed evaluation. The targeted physical examination will include body weight and assessment(s) of the body systems or organs, as indicated by subject symptoms, AEs, or other findings.

7.5.3. Vital Signs

Vital sign measurements include blood pressure, pulse, respiratory rate, and body temperature. Blood pressure and pulse will be taken with the subject in the recumbent, semirecumbent, or sitting position after approximately 5 minutes of rest. Clinically notable abnormalities that are considered clinically significant in the judgment of the investigator are to be reported as AEs.

7.5.4. Electrocardiograms

All 12-lead ECGs will be performed with the subject in a recumbent or semirecumbent position after 5 minutes of rest.

The 12-lead ECGs will be interpreted by the investigator at the site to be used for immediate subject management. The decision to include or exclude a subject or withdraw a subject from the study based on an ECG flagged as "Abnormal, Clinically Significant" is the responsibility of the investigator, in consultation with the sponsor's medical monitor, as appropriate. Clinically notable abnormalities that are considered clinically significant in the judgment of the investigator are to be reported as AEs.

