1.3.2.1. Pharmacokinetic/Pharmacodynamic Summary

INCB054828 exhibited linear PK over the dose range evaluated, with rapid oral absorption and a biphasic elimination, with a terminal half-life range of 10.9 to 31.4 hours. The projected average inhibition of FGFR2 based on PK and *in vitro* potency of INCB054828 ranged from 41% at 1 mg to 97% at 20 mg. Consistent with this projection, the observed inhibition of pFGFR2 in KATOIII cells spiked to *ex vivo* whole blood samples collected from subjects at trough was 82% after the 13.5 mg QD dose and 64% after the 9 mg QD dose. The steady-state plasma concentrations of INCB054828 after 13.5 mg QD dose that exceeded *in vivo* IC₅₀ over a 24-hour dosing period is showed in [Figure 1](#). The magnitude and frequency of HP was also dose-dependent. In the 9 mg cohort, 1 of 3 subjects developed HP in Part 1; 3 additional subjects were enrolled at 9 mg in Part 2. Of a total of 6 subjects administered 9 mg, 4 experienced HP; in the 13.5 mg cohort, all 6 subjects developed HP, which was managed with a low-phosphate diet and introduction of phosphate binders. Further, the increase in serum phosphorus observed after treatment with INCB054828 was exposure-dependent (see [Figure 2](#)).

Figure 1: INCB054828 Plasma Concentrations (Mean \pm SE) at Steady State After 13.5 mg QD Oral Doses of INCB054828

[figure not shown]
[figure not shown]

Figure 2: Serum Phosphate Versus Exposure

Therefore, based on a manageable safety profile and a favorable PK/PD profile, the targeted starting dose for this Phase 2 is 13.5 mg. This dose will be tested in 2 additional Phase 2 studies in subjects with bladder cancer (INCB 54828-201) and myeloproliferative neoplasms (INCB 54828-203).

Subjects will be monitored on an ongoing basis throughout this study as per the schedules of assessments (Table 5 and Table 6).

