5.2. Study Drug

5.2.1. INCB054828

5.2.1.1. Description and Administration

INCB054828 will be self-administered as a QD oral treatment on a 21-day cycle. Subjects will take study drug for 2 weeks continuously (14 days) followed by a 1-week (7 days) break. The starting dose will be 13.5 mg. Each dose of study drug should be taken immediately upon rising or after a 2-hour fast. Subject should plan to fast for 1 additional hour after taking study drug.

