5.4.4. Criteria for Permanent Discontinuation of Study Drug

The occurrence of unacceptable toxicity not caused by the underlying malignancy will be presumed to be related to study drug treatment and will require that the study drug be permanently discontinued. Unacceptable toxicity is defined as follows:

- Occurrence of an AE that is related to treatment with the study drug that, in the judgment of the investigator or the sponsor's medical monitor, compromises the subject's ability to continue study-specific procedures or is considered to not be in the subject's best interest.
- An AE requiring more than 2 dose reductions.
- Persistent AE requiring a delay of therapy for more than 21 days unless a greater delay has been approved by the sponsor.
- Increase in QT/QTcF to > 500 milliseconds or to > 60 milliseconds over baseline. In case of a QTc > 500 milliseconds, the subject must be hospitalized and a continuous ECG monitoring must be set up until the measure of the QTc interval decreases below 500 milliseconds and until acceptable in the opinion of a local cardiologist.

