6. STUDY ASSESSMENTS

All study assessments will be performed as indicated in the schedule of assessments ([Table 5](#)), and all laboratory assessments will be performed as indicated in [Table 6](#).

[Table 7](#) presents a summary of clinical laboratory analytes to be assessed. The order of assessments is suggested by the order of mention within the schedule. See Section 7 for instructions on each assessment. Further details of study procedures and assessments can be found in the study reference manual.

Table 5: Study Assessments

Procedure	Protocol Section	Pre-screening	Screening	Treatment				EOT	Follow-Up			Notes
				Days -28 to -1	Cycle 1		Cycle 2+		Safety	Disease Status	Survival	
			Day 1		Day 8 (± 3 days)	Day 15 (± 3 days)	Day 1 (± 3 days)					
			EOT + 30 (+5) days		Every 9 weeks	Every 12 weeks						
Genomic testing	7.1	X	X*								* May be done during prescreening or during screening.	
Informed consent	7.1	X	X									
Eye examination (includes slit lamp, visual acuity, funduscopy with digital imaging, and OCT)	7.5.5		X				X*	X				* Eye examination to be performed every 3 cycles (± 14 days) starting with Cycle 3 and/or as clinically indicated.
Review inclusion and exclusion criteria	3		X	X								
Demography and medical history	7.3		X									
Prior/concomitant medications	7.4		X	X	X	X	X	X	X			
Physical examination/ body weight, height	7.5.2		X*	X	X	X	X	X	X			* Comprehensive examination at screening, targeted physical examination thereafter.
Vital signs	7.5.3		X	X	X	X	X	X	X			
12-lead ECG	7.5.4		X	X		X	X	X	X			
ECOG status	7.6.2		X	X	X	X	X	X	X			

Table 5: Study Assessments (Continued)

Procedure	Protocol Section	Pre-Screening	Screening	Treatment				EOT	Follow-Up			Notes
				Days -28 to -1	Cycle 1		Cycle 2+		Safety	Disease Status	Survival	
			Day 1		Day 8 (± 3 days)	Day 15 (± 3 days)	Day 1 (± 3 days)					
			EOT + 30 (+5) days		Every 9 weeks	Every 12 weeks						
CT or MRI	7.6.1		X				X*	X		X**		* Every 2 cycles through Cycle 4; every 3 cycles thereafter starting with Cycle 7. ** Subjects who discontinue study treatment for a reason other than disease progression.
Review AEs	7.5.1		X	X	X	X	X	X	X			
Survival status	7.8.2										X*	* Once a subject has received the last dose of study drug, confirmed disease progression, or starts a new anticancer therapy.

CT = computed tomography; MRI = magnetic resonance imaging.

Table 6: Laboratory Assessments

	Protocol Section	Prescreening	Screening	Treatment				EOT	Follow-Up	Notes

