6.2. Treatment

The treatment period begins on the day that the subject receives the first dose of study drug (Cycle 1 Day 1) through the point at which the investigator determines that the subject will be permanently discontinued from study drug. Cycle 1 Day 1 must be no more than 28 days after the subject has signed the ICF and no more than 3 days after the date of enrollment. Dates for subsequent study visits will be determined based on this day and should occur within 3 days (+/-) of the scheduled date unless delayed for safety reasons. At Cycle 1 Day 1, results from screening visit evaluations should be reviewed to determine whether the subject continues to meet the eligibility requirements, as specified in the Protocol.

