7.7. Pharmacokinetic Assessments

7.7.1. Blood Sample Collection

Pharmacokinetic samples will be obtained on Cycle 1, Day 8 at predose, 1 to 2 hours postdose, and 4 to 12 hours postdose (3 samples total; Table 6). The exact date and time of the PK blood draws will be recorded in the eCRF along with the date and time of the last dose of study drug preceding the blood draw and the time of the most recent meal. Instructions for sample preparation and shipping to the central laboratory will be provided in the Laboratory Manual. The subject will receive a reminder card in advance of the study visit, providing instruction to hold the dose of study drug on the day of the visit, a place to record the time of the previous dose of study drug, and a place to record the time of the most recent meal or snack consumed.

On Cycle 1 Day 8, it is important to note that the subject must refrain from eating 8 hours prior to arriving at the site. The initial predose sample should be drawn approximately 1 hour before study drug administration. Subjects then need to fast for 1 additional hour after taking study medication. Once the subject takes the study drug, any subsequent timed samples will be taken.

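### No on-study ECG is scheduled or required at steady-state peak exposure, and the one visit with timed postdose PK samples (Cycle 1 Day 8) has no ECG

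*Protocol*

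**What the plan says.** **Dosing.** Protocol 5.2.1.1: "Subjects will take study drug for 2 weeks continuously (14 days) followed by a 1-week (7 days) break". Days 1 to 14 of each cycle are on drug and Days 15 to 21 are off. SAP 4.1.5 ties Day 1 of each cycle to the first dose of that cycle.

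**ECG schedule.** The ECG row of Table 5 (Protocol 6) has six marks: "12-lead ECG 7.5.4 X X X X X X". They stand under screening, Cycle 1 Day 1, Cycle 1 Day 15, Cycle 2+ Day 1, end of treatment and safety follow-up. The vital signs row of the same table has seven: "Vital signs 7.5.3 X X X X X X X". The extra mark is Cycle 1 Day 8, so that is the blank cell in the ECG row.

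**ECG conditions.** Protocol 7.5.4: "All 12-lead ECGs will be performed with the subject in a recumbent or semirecumbent position after 5 minutes of rest". No time relative to dose is given there or elsewhere.

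**Visit window.** Under Protocol 6.2, visits "should occur within 3 days (+/-) of the scheduled date unless delayed for safety reasons". Cycle 1 Day 15 may therefore fall on Days 12 to 18.

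**PK sampling.** Protocol 7.7.1: "Pharmacokinetic samples will be obtained on Cycle 1, Day 8 at predose, 1 to 2 hours postdose, and 4 to 12 hours postdose". Day 8 is the only PK day.

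**Use of the ECGs.** Protocol 5.4.4 lists among its discontinuation criteria "Increase in QT/QTcF to > 500 milliseconds or to > 60 milliseconds over baseline". SAP 8.5 summarises QTcF values and changes from baseline at each scheduled visit, and SAP 4.1.6 assigns results to the nominal visit with no further windowing.

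**The concern.** If a drug's effect on QTcF follows its concentration, the informative ECG is one taken near peak concentration after accumulation. Here the nominal on-treatment ECG days are a first-dose day, a day about 24 h after the last dose, and days that follow a week off drug. The visit with known dose times, measured concentrations and near-complete accumulation has no ECG.

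Three things are at stake. First, the by-visit QTcF tables could show little change because of when the traces were taken, and nothing in SAP 8.5 would tell a reader so. Second, scheduled detection of a value that meets a 5.4.4 criterion relies on the same traces. Third, if exposure-response for safety is pursued (Protocol 9.4.3, SAP 7.6), no scheduled ECG is paired with a measured concentration.

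**Working it through.** The plan states no figure on this point to reproduce. The check sets the calendar against the dosing cycle and then scales exposure.

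**Inputs.** Protocol 1.3.2.1 gives "a terminal half-life range of 10.9 to 31.4 hours". Doses are 24 h apart on Days 1 to 14. ECG and PK days are as listed above.

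**Assumptions.** One compartment, instantaneous absorption, and the terminal half-life governing the whole decline.

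**Formulas.** With r = 0.5^(24/t½):
- peak after dose n, as a fraction of steady-state peak: 1 − r^n
- level h hours after the Day 14 dose: (1 − r^14) × 0.5^(h/t½)
- accumulation: 1/(1 − r)

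For t½ = 10.9 h, r = 0.217; for t½ = 31.4 h, r = 0.589.

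| Time point | Fraction of steady-state peak, t½ = 10.9 h | t½ = 31.4 h | ECG in Table 5? |
|---|---|---|---|
| Cycle 1 Day 1, postdose (0 if predose) | 78% | 41% | yes, untimed |
| Cycle 1 Day 8, postdose | 100% | 98.6% | **no** |
| Days 12–14, postdose | 100% | 99.8–99.9% | only through the Day 15 window |
| Days 12–14, predose | 22% | 59% | only through the Day 15 window |
| Day 15 nominal (24 h after last dose) | 22% | 59% | yes |
| Day 18, late end of window (96 h) | 0.2% | 12% | through the window |
| Cycle 2 Day 1 nominal, predose (192 h) | below 0.001% | 1.4% | yes, untimed |
| Cycle 2 Day 1 nominal, postdose | 78% | 43% | yes, untimed |

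The 1.4% is for the nominal date. At the early end of the Cycle 2 Day 1 window (study Day 19) the predose level is 0.05% to 7.1%.

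**Accumulation missed by a postdose Day 1 ECG.** 1/(1 − 0.217) = 1.28 and 1/(1 − 0.589) = 2.43, so 1.3- to 2.4-fold under the one-compartment assumption.

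**Effect of biphasic elimination.** Protocol 1.3.2.1 describes elimination as biphasic but does not give the share of the peak carried by the terminal phase. As an illustration, let that share be one half, with the first phase gone by 24 h and t½ = 31.4 h:
- accumulation at peak = 0.5 + 0.5 × 2.43 = 1.72, not 2.43
- first-dose peak = 1/1.72 = 58% of steady-state peak, not 41%
- Day 15 level = (0.5 × 2.43 × 0.589)/1.72 = 42%, not 59%

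So 2.4-fold is an upper bound, and a postdose Day 1 ECG may come closer to peak than the table shows. Day 15, by contrast, falls further below peak.

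**Day 8 window.** Days 5 to 11 are all dosing days. In the least favourable case (Day 5, t½ = 31.4 h) the postdose peak is 1 − 0.589^5 = 93% of steady state.

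**The case against.** No document requires a peak-exposure ECG, and characterising QT is not a study objective. SAP 8.5 is descriptive and does not claim to estimate a QTcF effect. This stands: the point is a design improvement, not a contradiction between passages.

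A reader might infer more than the documents support:

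- **That Day 15 is drug-free.** No dose is due, but 22% to 59% of the postdose level remains. It is a steady-state trough, and three of the seven permitted dates (Days 12 to 14) are dosing days. An on-drug trace is possible, but only by chance and untimed.
- **That every end-of-treatment ECG is off drug.** That visit follows the decision to stop (Protocol 6.2, 6.3). If the stop comes mid-block, the trace may fall soon after a dose.
- **That a planned analysis is defeated.** Exposure-response for safety is only to be considered if data suffice, and QTcF is not named.
- **That the drug prolongs QTcF.** Nothing in the documents shows this. The Phase 1 adverse event rows that could be read list no QT event, and whether sparse ECGs suffice also depends on earlier QT data that these documents do not contain.

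There are mitigations. A screening QTcF above 450 ms is an exclusion (Protocol 3.2), and unscheduled visits are allowed when medically warranted (6.6). The latter would not find silent prolongation.

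It is also fair that moving one trace leaves later cycles as they are. Average participation of about 6 months (Protocol 4.4) spans at most 6 × 30.4375/21 ≈ 8.7 cycles, and from Cycle 2 the only scheduled on-treatment ECG in each would still be on Day 1.

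**Conclusion.** The point holds as a matter of detection. No on-study ECG is scheduled or required at steady-state peak, and none is paired with a PK sample. Nominal exposure at the scheduled traces is a trough (Day 15), at most about 1.4% of peak (later Day 1, predose), or a first dose without accumulation (any Day 1, postdose). Day 8 would give 98.6% to 100%.

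The calendar facts are certain. The percentages rest on the one-compartment approximation; biphasic elimination lowers the Day 15 figure and makes the 1.3- to 2.4-fold accumulation an upper bound. The consequence is limited ability to detect, or to rule out, an exposure-related QTcF change. It is not evidence that such a change exists. The change below is worth making because it costs little.

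**What to change.** **Protocol.** In Table 5, move the Cycle 1 Day 15 ECG to the existing Cycle 1 Day 8 visit. In 7.5.4, state that it is taken at the 1 to 2 h postdose PK sample with clock times of ECG and dose recorded, and that the Cycle 1 Day 1 ECG is predose. The latter also settles whether that trace belongs in the baseline, since SAP 8.5 averages all values before the first dose. The documents give no time of peak in their text; the 1 to 2 h choice rests on the rapid absorption described in 1.3.2.1 and on a sample that is already taken.

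**SAP 8.5.** Report QTcF change at Cycle 1 Day 8 separately, and label Cycle 2+ Day 1 values as following the off-drug week. The labelling applies even if all subjects have completed Cycle 1.

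**Cost.** One amendment to Table 5 and 7.5.4 and a short SAP addition; no new visit and no added procedure. The trace at the end of the dosing block is lost, so an effect that emerges late in the block would be less visible. If the sponsor wants to keep it, the alternative is one additional ECG on Day 8. Monitoring from Cycle 2 on is unchanged, and the 5.4.4 thresholds are not touched.

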7.5.5. Comprehensive Eye Examination

A comprehensive eye examination should be performed by a qualified ophthalmologist at screening, once every 3 cycles (\pm 14 days, starting at Cycle 3), at EOT, and as clinically indicated. The eye examination should include a visual acuity test, slit-lamp examination, funduscopy with digital imaging, and OCT. Every effort should be made to ensure that all subsequent examinations are performed by the same ophthalmologist.

7.5.6. Laboratory Assessments

Each site's local laboratory will be used for eligibility and ongoing safety assessments. Chemistry, hematology, coagulation panel, lipid panel, serology, endocrine function, and urinalysis will all be analyzed by each site's laboratory.

7.5.6.1. Pregnancy Testing

A serum pregnancy test will be required for all women of childbearing potential during screening. A urine pregnancy test is allowed on Day 1 (before the first dose of study drug), Day 1 of each subsequent cycle, and at the EOT visit. Urine pregnancy tests will be conducted as outlined in [Table 6](#), as medically indicated, or per country-specific requirement. Urine pregnancy tests will be performed locally. If a urine pregnancy test is positive, the results should be confirmed with a serum pregnancy test.

If the serum pregnancy test is negative after a urine test was positive, then the investigator will assess the potential benefit/risk to the subject and determine whether it is in the subject's best interest to resume study drug and continue participation in the study.

7.5.6.2. Hepatitis Screening Tests

Subjects will undergo screening for hepatitis B or C through their local laboratory. If the results are positive, then subjects will be required to undergo additional testing. Subjects with chronic or cleared hepatitis B or C will be allowed to enroll. Chronic is defined as subjects with no evidence of liver cirrhosis or active hepatitis (elevation of transaminases) but with positive anti-HCV antibody test or positive HCV RNA, positive HBV surface antigen, or positive HBV DNA.

7.5.6.3. HIV Screening Tests

Subjects outside of the US will be required to submit to an HIV test during screening to ensure negative HIV status before enrollment/Cycle 1 Day 1. This test is optional for US subjects.

7.5.6.4. Evaluation of FGF and FGFR Genetic Alterations

All potential subjects must be evaluated for FGF/FGFR alteration status before enrollment. Subject eligibility can be based on local genomic testing results, if available. Confirmatory testing through the central genomics laboratory will be performed on all subjects. See [Appendix D](#) for a list of alterations.

